IPM 034, the fifth trial of Ring-004 was a Phase I open-label, parallel group trial, to assess the release profile of Ring-004 over extended periods of ring use in HIV-negative women, 18 to 40 years of age. The trial was conducted at a Phase I unit in Belgium and enrolled 40 women in five groups (Groups A, B, C, D and E) of eight women each. Each woman was administered with one dapivirine ring and instructed to wear the ring continuously for a period of 7, 14, 28, 56, or 84 days (1, 2, 4, 8, or 12 weeks). One SAE (thoracic vertebral fractures following a motor vehicle accident) was reported in a participant using the dapivirine ring in Group C. The event was assessed as severe (Grade 3) and regarded by the Investigator as unrelated to the IP. Product-related TEAEs were reported for four women during the trial of whom three experienced mild vaginal discharge (one woman with a 56-day ring use period and two women with an 84-day ring use period) and one experienced moderate bacterial vaginitis (84-day ring use period). Based on all safety evaluations performed during the trial, no overall clinically significant differences were observed between the different ring use periods.

MTN-013/IPM 026, a Phase 1 safety and pharmacokinetics study of dapivirine VR, maraviroc VR, dapivirine/maraviroc VR and placebo VR, enrolled approximately 48 women between the ages of 18-40. The participants were randomized in a 1:1:1:1 ratio to 28 days of continuous study vaginal ring use. Over the course of 52 days, 14 follow-up visits occurred. There was no statistically significant difference in the number of participants with genitourinary AEs between placebo arm and any other treatment arms. Twenty-two women experienced 33 grade 1 and one grade 2 related genitourinary AEs.¹² Two grade 2 AEs were determined to be related to study product. At Day 28, dapivirine vaginal fluid levels were 14.9 μ g/mL in women assigned to the dapivirine only ring.

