10 STATISTICAL CONSIDERATIONS

10.1 Overview and Summary of Design

This is a multi-site, double-blinded, two arm, 3:1 randomized, placebo-controlled trial to assess the safety of dapivirine (25 mg) administered in a silicone elastomer vaginal ring, when inserted once every 4 weeks during 24 weeks of study product use by healthy, HIV-uninfected, sexually experienced, adolescent females, 15 - 17 years old (inclusive), as compared with a placebo VR. A total of approximately 96 adolescent females (72 in the dapivirine VR arm and 24 in the placebo VR arm) will be randomized.

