Approximately 36 women randomized to active ring will provide vaginal fluid swabs that will be weighed. From previous clinical trials with dapivirine Ring-004 (IPM 013 and IPM 024), the inter-participant CV% of vaginal fluid concentrations of dapivirine prior to ring removal on Day 28 ranged from 35% to 85%, depending on sampling location. If one assumes a CV% of 70%, and comparison of MTN-013/IPM 026 (N=12) to MTN-023/IPM 030 (N=36), then with 5% type I error and 80% power, we can exclude a difference as large as 0.95 SD units or a 67% difference.¹¹ These historical data for comparison are considered known and fixed. Approximately 36 women randomized to active ring will provide vaginal fluid swabs that will be not be weighed, given logistical constraints, however, these swabs will be analyzed for drug concentration without correction for weight. The variability of drug concentration from the unweighed swab cohort will be compared to the variability in the weighed swab cohort.

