10.8.3 Secondary Analyses

Acceptability

To assess acceptability of the study products, summary statistics will be calculated on each component of acceptability by arm.

Adherence

The average rate of VR use will be calculated in both arms along with 95% confidence intervals. These rates will be based on participant's self-report of product use at monthly clinic visits. The difference between adherence rates with its corresponding 95% confidence interval will be used to assess adherence of the study product compared to placebo.

Pharmacokinetics

A population mean and standard deviation of the end-of-period dapivirine concentrations for each woman in each 28-day period will be calculated based on the samples obtained as described above. The population mean from this study will be compared to the population mean and standard deviation from similar end of period dapivirine results for each matrix – plasma and vaginal fluid– in MTN-013/IPM 026, IPM 024, and IPM 013.

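### Section 10.8.3 does not limit the vaginal-fluid mean to weight-corrected swabs, and the weighed/unweighed variability check compares two different groups of women

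*Protocol*

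**What the plan says.** Section 10.1 randomizes "72 in the dapivirine VR arm and 24 in the placebo VR arm". The Pharmacokinetic Endpoint text in Section 10.4.2 divides the active arm in two: "Approximately 36 women randomized to active ring will provide vaginal fluid swabs that will be weighed", and "Approximately 36 women randomized to active ring will provide vaginal fluid swabs that will be not be weighed, given logistical constraints". For the second group, "these swabs will be analyzed for drug concentration without correction for weight".

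The power statement in that section compares MTN-013/IPM 026 (N=12) with this trial at N=36, not 72. It assumes a CV of 70%, 5% type I error and 80% power, and gives 0.95 SD or 67%. The paragraph ends: "The variability of drug concentration from the unweighed swab cohort will be compared to the variability in the weighed swab cohort". Section 10.4.2 also calls the PK endpoint a description, says the comparison with adults is descriptive, and says vaginal fluid is collected from all 96 participants.

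Section 10.8.3 states: "A population mean and standard deviation of the end-of-period dapivirine concentrations for each woman in each 28-day period will be calculated", on the basis of the samples described earlier. It continues: "The population mean from this study will be compared to the population mean and standard deviation from similar end of period dapivirine results for each" of the two sample types, plasma and vaginal fluid, in three adult ring studies. It sets no limit to weighed swabs and no separate reporting of the two cohorts.

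Section 2.6.1 gives the adult benchmark from MTN-013/IPM 026 per volume of fluid: "At Day 28, dapivirine vaginal fluid levels were 14.9" μg/mL.

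**The concern.** Without a weight, the quantity of fluid on the swab is unknown. The assay result is then not expressed per unit of fluid and is on a different scale from a weight-corrected value. This is an inference from the stated lack of correction, but a direct one.

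Two problems follow.

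- **Analysis set.** The two sections do not agree on who enters the vaginal-fluid mean. An analyst who follows 10.8.3 as written would average corrected and uncorrected values, and the SD would carry the variation in how much fluid each swab picked up. Section 10.4.2 says the aim is to find out whether adolescent concentrations differ from adult ones, and Section 2.8.2 says further studies may be considered if they do. The summary therefore has a use.
- **Variability check.** The two cohorts are different women, separated for logistical reasons. A difference in spread could come from the women, their adherence or the collection technique. Equal spread could hide a real loss of precision. Comparing spread also says nothing about the level of the unweighed results.

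**Working it through.** **Inputs.** From 10.1 and 10.4.2: 36 + 36 = 72 active-arm women; 12 historical adults; CV 70%; 5% type I error (sidedness not stated, two-sided used); 80% power. The protocol gives no figure for swab-weight variability, so its CV is assumed and shown from 20% to 70%.

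**1. Which women does the stated figure cover?** For a two-sample comparison of 12 versus 36, the normal approximation gives (1.960 + 0.842) × √(1/12 + 1/36) = 2.802 × 0.333 = 0.934 SD. The noncentral t with 46 df gives 0.954 SD, and 0.954 × 70% = 66.8%. This reproduces 0.95 SD and 67%, so 10.4.2 counts only the weighed women.

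With 12 versus 72 on a common scale, the normal figure would be 2.802 × √(1/12 + 1/72) = 0.874 SD (t: 0.884). Leaving out the unweighed swabs therefore costs little precision.

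**2. Chance range of the variability check.** On the log scale, Var(log s) ≈ 1/[2(n − 1)].

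- Two separate groups of 36: SE of log(s₁/s₂) = √(1/35) = 0.169. With no true difference, the 95% range of the SD ratio is exp(±1.96 × 0.169) = 0.72 to 1.39.
- The same 36 swabs, corrected and uncorrected: SE = √[(1 − r²)/35]. At r = 0.8 this is 0.101, range 0.82 to 1.22. At r = 0.9 it is 0.074, range 0.87 to 1.16. Both correlations are assumed.

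**3. Size of the effect to be seen.** Assume log-normal values, a true fluid CV of 70%, and weight independent of concentration. Then σc² = ln(1.49) = 0.399 and σw² = ln(1 + CVw²). The uncorrected CV is √[1.49(1 + CVw²) − 1], the log-SD ratio is √(1 + σw²/σc²), and the correlation is its reciprocal. Power for separate cohorts is from a two-sided F test on log variances (35, 35 df). Power for the paired check is from a simulated Pitman-Morgan test on logs (n = 36, 20,000 replicates).

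| Assumed weight CV | Uncorrected CV | Log-SD ratio | Correlation | Power, separate cohorts | Power, paired |
|---|---|---|---|---|---|
| 20% | 74% | 1.05 | 0.95 | 6% | 15% |
| 30% | 79% | 1.10 | 0.91 | 9% | 26% |
| 40% | 85% | 1.17 | 0.85 | 15% | 41% |
| 50% | 93% | 1.25 | 0.80 | 25% | 57% |
| 70% | 110% | 1.41 | 0.71 | 52% | 80% |

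The correlations of 0.9 and 0.8 in step 2 correspond to weight CVs of about 30% and 50%. At both, the expected ratio (1.10 and 1.25) lies well inside the 0.72 to 1.39 chance range. The separate-cohort check reaches 80% power only at a log-SD ratio of about 1.62 (variance ratio 2.61).

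**The case against.** A reader might infer that the protocol definitely pools all swabs and that the adult comparison is therefore meaningless. The text does not go that far. Section 10.8.3 refers back to the samples described earlier, the only vaginal-fluid comparison sized there is the weighed 36, and the benchmark is to be similar results for each matrix. Taken wholly literally, the sentence would also take in the placebo women, which cannot be meant. A weighed-only intention is plausible. What remains is that 10.8.3 does not say so, and anyone following its wording would pool.

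A reader might also infer that the weighed/unweighed split follows site. The protocol gives only logistical constraints as the reason and does not say how women are allocated. Confounding needs only that allocation to weighing is not stated to be random.

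A third tempting reading is that the variability check decides whether unweighed swabs are adequate. No test, criterion or decision rule is attached to it, and the PK endpoint is described as descriptive. That objection stands: the planned comparison may stay as a description.

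The paired alternative also has limits. It is often inconclusive when swab weights vary little. Pitman-Morgan is meaningful here only on logs, because the two values have different units. It uses weighed-cohort swabs only, so it does not show how swabs in the unweighed cohort behaved. Sample handling is left to a procedures manual that is not shown.

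A later analysis plan could settle the analysis set, but the wording it would inherit is stated in the protocol and points the wrong way.

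**Conclusion.** The point holds as an inconsistency between two sections and a weak choice of comparison. Section 10.4.2 sizes the vaginal-fluid comparison on about 36 weighed women. Section 10.8.3 does not exclude the roughly 36 active-arm women whose values are uncorrected.

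The between-cohort check mixes differences between women with the effect of weighing. It has about 6% to 15% power for assumed weight CVs of 20% to 40%, against 15% to 41% when the same swabs are computed both ways. Over the full 20% to 70% range the figures are 6% to 52% and 15% to 80%. They rest on log-normal values, the protocol's 70% CV, and swab weight independent of concentration.

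The documents do not establish that pooling is intended, that the split is by site, or that any decision hangs on the check. The point concerns vaginal fluid only, within a secondary, descriptive endpoint.

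**What to change.** In 10.8.3, state that the vaginal-fluid mean, SD and adult comparison use weight-corrected swabs from active-arm women only (N about 36, matching 10.4.2). Tabulate the unweighed swabs separately as uncorrected values. The plasma analysis can stay as it is.

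In 10.4.2, add a paired log-scale comparison of corrected and uncorrected values from the same weighed swabs, either as a ratio of log SDs with its interval or as a Pitman-Morgan test on logs. Keep the between-cohort comparison and label it descriptive. State that the paired result does not describe the unweighed cohort's swabs.

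The cost is wording in the protocol or analysis plan. The uncorrected value of a weighed swab exists before division by its weight, so no extra sample or assay is needed.

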10.5 Participant Accrual, Follow-up and Retention

Based on previous studies of vaginal products, the accrual of 96 eligible participants will take approximately 12 months per site. Participants lost to follow-up and/or on temporary hold or permanent product discontinuation will not be replaced. The team will consider a participant "lost to follow-up" for this trial if she has missed two consecutive study visits and is unreachable by clinic staff after at least three contact attempts. However, every effort will be made to complete their regularly scheduled safety evaluations. Additionally, participants who are found to be HIV-infected and/or pregnant after enrollment will be terminated from the study and will not be replaced. Each site will target retention of 95% of enrolled participants over the 25-Week follow-up period.

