7.5.2 Participants Who Become Pregnant

Study staff, with written permission from the participant and the participant's parent and/or guardian, may contact the medical care provider to inform him/her of the participant's involvement in MTN-023/IPM 030.

Participants will be permanently discontinued from VR use and will be instructed to return the study VR. The participant will be offered the option to continue follow-up visits per her original study schedule until her originally scheduled study exit date. For those who choose to remain in follow-up, protocol-specified procedures will continue except the following:

- hCG testing*
- Samples for PK*
- Provision of contraceptive counseling
- Provision of study product and associated procedures
- Provision of product adherence counseling
- Pelvic exams, unless required for AE follow-up

*Perform at the first visit where study product is discontinued, but omit at subsequent visits.

Pregnancy outcomes will be reported on relevant CRFs for participants found to be pregnant at the 24-Week Final Clinic Visit/Early Termination Visit.

Participants who become pregnant while on study product may be offered enrollment in MTN-016 (www.mtnstopshiv.org), provided their study site is taking part in MTN-016.

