8.5 Pregnancy and Pregnancy Outcomes

Pregnant females are excluded from this study. If participants become pregnant at any time during the course of the study, participants will be offered the option to remain in the study, but off of study product, per Section 7.5.2.

Pregnancy-related data will be collected using pregnancy CRFs for all pregnancies detected during the study. Pregnancy outcomes will not be expeditiously reported to IPM, DAIDS MO, and NICHD MO unless there is an associated AE in the pregnant participant that meets expedited reporting criteria or the pregnancy results in a

congenital anomaly meeting International Conference on Harmonisation (ICH) guidelines for expedited reporting.

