9.7 HIV-1 Infection

A participant who has a positive test for HIV-1 must have study product held. If the participant is subsequently determined to be HIV-negative according to the algorithm in Appendix II, study product may be resumed. If HIV-1 infection is confirmed, study product will be permanently discontinued by the IoR/designee. A participant who is confirmed to be HIV-1 positive during the course of the study will have study product discontinued and will be followed, as per Section 7.5.1.

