9.8 Pregnancy

All study participants are required to be using an effective method of contraception according to Section 5.2. Study staff will provide contraceptive counseling to enrolled participants throughout the duration of study participation and will facilitate access to contraceptive services through direct service delivery. Study staff also will provide participants with condoms and counseling on use of condoms ideally during every sex act during study participation.

Pregnancy testing is performed at all study visits and may be performed as indicated at interim visits. In addition, participants are encouraged to report all signs or symptoms of pregnancy to study staff. The IoR/designee will counsel any participant who becomes pregnant regarding possible risks to the fetus according to site SOPs. The IoR/designee also will refer the participant to all applicable services; however, sites will not be responsible for paying for pregnancy-related care.

A participant who is pregnant at the Final Clinic Visit will continue to be followed until the pregnancy outcome is ascertained (or, in consultation with the PSRT, it is determined that the pregnancy outcome cannot be ascertained). Pregnancy outcomes are reported on relevant CRFs; outcomes meeting criteria for EAE reporting also are reported on EAE forms.

A participant who becomes pregnant during the course of the study will have study product discontinued and will be followed, as per Section 7.5.2.

A participant who becomes pregnant during the course of study participation may be offered participation in MTN-016, HIV Prevention Agent Pregnancy Exposure Registry: EMBRACE Study, at sites participating in MTN-016. This registry study captures pregnancy outcomes as well as infant health information, (including growth), to evaluate the safety and teratogenic risks of microbicide and oral PrEP exposure in pregnancy. In the event that a study site is not taking part in MTN-016, participants may be contacted to collect pregnancy outcomes.

For additional details regarding obtaining pregnancy outcome, please reference the MTN-023/IPM 030 SSP Manual (www.mtnstopshiv.org).

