10.8.2 Primary Analysis

When the use of descriptive statistics to assess group characteristics or differences is required, the following methods will be used: for categorical variables, the number and percent in each category; for continuous variables, the mean, median, standard deviation, quartiles and range (minimum, maximum). Within-treatment group assessment of the change from the baseline measurement to a follow-up measurement will be analyzed using McNemar's test (for categorical response variables) or the paired t-test or Wilcoxon signed-ranks test (for continuous variables). When use of formal testing to assess differences between users of the placebo VR and users of the dapivirine VR is required, the following methods will be used: for binomial response variables, chi-square tests and logistic regression (or exact testing methods); for continuous variables, t-tests and linear regression or nonparametric methods if data are non-Normal.

To assess the adequacy of the randomization, participants in each of the two arms will be compared for baseline characteristics including demographics and laboratory measurements using descriptive statistics.

Safety Endpoints

All females randomized into the study will be included in the primary analysis according to principle of Intent-to-Treat. To assess safety, the number and the percentages of participants experiencing each safety endpoint will be tabulated by study arm. Each participant will contribute once in each category (i.e., only for the highest severity AE for each participant) for the calculation of event rates. Exact binomial confidence intervals will be calculated for each safety endpoint for each arm and Fisher's exact test used to test for differences in event rates between the two arms.

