13.7 Special Populations

13.7.1 Pregnant Females

Females who test positive for pregnancy at Screening or Enrollment Visits will not be eligible to participate in this study. Should a participant test positive for pregnancy after Enrollment, a product hold will be implemented but all follow-up visits will be completed and data collected per Section 7.5.2. A urine pregnancy test will be performed on all women at scheduled study visits, and additionally at interim visits as indicated; the IoR/designee will discontinue study product among participants who test positive for pregnancy. During the informed consent process, females will be informed that study VR is not a method of contraception and the effects of the study VR on a developing human fetus are unknown.

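### Section 10.5 ends study participation at pregnancy or HIV infection, while seven other sections stop product but offer or require continued follow-up; the rules need to be reconciled

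*Protocol*

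**What the plan says.** Section 10.5, on accrual, follow-up and retention, says that "participants who are found to be HIV-infected and/or pregnant after enrollment will be terminated from the study and will not be replaced".

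The sections that govern visits and management say something different.

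- **Pregnancy.** Section 7.5.2 permanently stops ring use and then says: "The participant will be offered the option to continue follow-up visits per her original study schedule until her originally scheduled study exit date". Section 8.5 says "participants will be offered the option to remain in the study, but off of study product, per Section 7.5.2". Section 9.8 says that a participant who becomes pregnant "will have study product discontinued and will be followed, as per Section 7.5.2". Section 13.7.1 goes further and says "all follow-up visits will be completed and data collected per Section 7.5.2".
- **HIV infection.** Section 7.5.1 makes the same offer of follow-up as 7.5.2. Section 9.7 says that a confirmed case "will have study product discontinued and will be followed, as per Section 7.5.1". Section 13.10.2 also sends the reader to 7.5.1.
- **General rules.** Section 7.5 encourages anyone who stops product to stay for safety evaluations. Section 9.9, which sets the criteria for early termination, names neither pregnancy nor HIV infection.

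Section 10.8.2 fixes the primary analysis: "All females randomized into the study will be included in the primary analysis according to principle of Intent-to-Treat". Section 10.2 defines the primary endpoints as the proportions of participants with related Grade 2 events and with Grade 3 or higher events.

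**The concern.** Two instructions on the same question are in force, and a site can comply with only one. A site that follows 10.5 stops collecting adverse events soon after the diagnosis. A site that follows 7.5.1 or 7.5.2 goes on collecting them, if the participant agrees, to her scheduled exit date. The primary endpoints are adverse-event proportions over about 25 weeks, and the Grade 3 or higher endpoint is not limited to related events. Completeness of the primary safety data after a post-randomization event would therefore depend on which section a site reads.

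The reporting window is affected too. Under 8.4.4 the expedited reporting period runs to the 25-week call or study termination. After that, unless otherwise noted, only suspected unexpected serious adverse reactions that staff learn of passively are reported. Ending participation at the diagnosis can close that window early, at a time when safety information on an exposed participant is of particular interest.

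The same paragraph of 10.5 sets a 95% retention target. It does not say whether a participant terminated under its own rule counts as a loss.

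**Working it through.** The point is mainly textual, so the first check sets the passages side by side.

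**1. Can 10.5 be read as stopping product only?** No. The same paragraph refers separately to temporary hold and permanent product discontinuation when it says who will not be replaced. It then adds termination from the study for HIV infection and pregnancy as a further case.

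**2. How many sections disagree with 10.5?** For HIV infection: 7.5.1, 9.7 and 13.10.2. For pregnancy: 7.5.2, 8.5, 9.8 and 13.7.1. That makes 3 + 4 = 7 specific sections, plus the general rule in 7.5. No sentence reconciles them or states precedence.

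**3. Do those seven agree among themselves?** Not fully. Sections 7.5.1, 7.5.2 and 8.5 make follow-up an option offered to the participant. Section 13.7.1 states that all follow-up visits will be completed.

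**4. What changes in the analysis?** Section 10.8.2 includes all randomized participants, so the set (72 + 24 = 96) is unchanged. The operating characteristics in 10.4.1 stand as printed. For example, the exact 95% interval for 0/72 recomputes to (0, 4.99%). With a placebo rate of 1/24, Fisher's exact test at two-sided 0.10 has power 80.3% at 26.3% and 90.2% at 30.2%, against the stated 80% and 90%. None of these figures depends on how the contradiction is resolved. Only event capture after the diagnosis differs.

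**5. Retention.** Pooled over sites, 95% × 96 = 91.2, so at least 92 must be retained and at most 4 lost.

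- 4 lost: 92/96 = 95.8%.
- 5 lost: 91/96 = 94.8%.

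If terminations under 10.5 count as losses, five of them would miss the pooled target with no other dropout. The protocol sets the target by site, so this is only an indication of scale.

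**6. How long could follow-up be cut short?** Scheduled testing limits this. The first follow-up pregnancy test is at Week 2, which leaves at most 25 − 2 = 23 weeks. Routine follow-up HIV serology is at Weeks 12 and 24 (elsewhere only if indicated), which leaves 25 − 12 = 13 or 25 − 24 = 1 week. An early termination visit with the call one week later (7.4.5, 7.4.6) would recover about one of those weeks.

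**7. Follow-up time at stake.** The protocol gives no expected pregnancy or HIV incidence. I assume that 2%, 5% or 10% of participants are affected and that they stop at Week 12. Planned follow-up is 96 × 25 = 2,400 person-weeks.

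- 2%: 0.02 × 96 × 13 = 25.0 person-weeks, 1.0% of 2,400.
- 5%: 0.05 × 96 × 13 = 62.4 person-weeks, 2.6%.
- 10%: 0.10 × 96 × 13 = 124.8 person-weeks, 5.2%.

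With stops at Week 20 or Week 4 instead, the range over the same rates is 0.4% to 8.4%. These are upper figures for the difference between the readings, because follow-up under 7.5.1 and 7.5.2 is optional.

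**The case against.** The strongest reply is that 10.5 is one sentence in a paragraph about accrual and replacement, while every visit and management section points the other way. Sites work from Sections 7 and 9 and would probably keep following these participants. That makes divergence less likely. It does not remove the contradiction, because 10.5 is current text, is worded as a rule and is not subordinated to anything.

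The second reply is that few participants are likely to be affected. Section 5.2 requires effective contraception for at least 30 days before Enrollment and agreement to use condoms. Section 5.3 excludes those with a known HIV-infected partner or with three or more partners in the month before Screening. This stands, and the number may well be small.

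Third, the other sections do not guarantee the data either. Follow-up is mostly an offer, and 7.5.1 and 7.5.2 drop pelvic examinations unless an adverse event requires them. Ascertainment of genital events therefore falls under either rule. This stands and limits what is lost by following 10.5.

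Fourth, 10.8.4 plans adjusted secondary analyses and sensitivity analyses that impute under extreme scenarios. These lessen the effect on interpretation but cannot recover events that were never collected.

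A reader might go further and infer that truncated participants would be counted as event-free. Section 10.8.2 does not say so. It tabulates participants with events and is silent on incomplete follow-up, and 10.8.4 addresses missing data separately. A reader might also set one lost placebo participant, 1/24 = 4.2%, against the placebo event rate in the power example. That compares unlike things: a participant with shortened follow-up is not a safety event and keeps the data collected before her diagnosis.

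**Conclusion.** The contradiction is real and, as written, leaves a conduct rule undetermined in a trial whose primary endpoints are adverse-event proportions. Its reach is limited to three things: capture of related Grade 2 and of Grade 3 or higher events after the diagnosis, the length of the reporting window in 8.4.4, and possibly the retention count. The intent-to-treat set, its denominator and the sample-size tables are unaffected.

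The size cannot be fixed from the protocol. Under the assumed 2% to 10% affected at Week 12, at most about 1.0% to 5.2% of planned follow-up time is at stake, and the true figure may be lower. The documents do not support the inference that the loss would bias the comparison between arms. Nothing indicates that pregnancy or HIV infection, or a site's choice of section, would differ by arm, and randomization is stratified by site. The supportable concern is incomplete and site-dependent capture of safety data. A statistical analysis plan cannot repair this, because it cannot restore visits that did not take place.

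**What to change.** Reconcile 10.5 with 7.5, 7.5.1, 7.5.2, 8.5, 9.7, 9.8, 9.9, 13.7.1 and 13.10.2 so that one rule applies at all sites. The reconciliation should also settle whether follow-up is offered (7.5.2) or expected in full (13.7.1). Which clinical rule applies is for the protocol team to decide.

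State stopping of product and termination from the study separately. For example, 10.5 could refer to 7.5.1 and 7.5.2 for what happens to these participants and keep only the statement that they are not replaced. Add that they remain in the intent-to-treat safety analysis, and say whether they count as losses against the 95% target.

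The cost is a short protocol clarification. If continued follow-up is confirmed, no new visits are needed, because the existing schedule already provides for them. Sample size, endpoints and tests do not change.
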